### **9.3 Outliers**

Scatter plots will be examined to identify potential outliers in any of the continuous variables identified in [Section 4](#). Frequencies of the categorical data listed in [Section 4](#) will be examined to identify questionable values. Before data snapshot the validity of any questionable values will be verified and observations found to be due to data entry errors will be corrected by the study team. Potential outliers that are not due to data entry error will be included in the analysis. No valid measurement will be purposely excluded from descriptive or inferential analyses. However, sensitivity analyses may be conducted to evaluate the influence of extreme values in the data. These analyses will be documented in the clinical study report.

### **9.4 Distributional Characteristics**

The assumptions underlying the parametric models analyzed for continuous data will be checked. In cases where residuals indicate marked departures from the assumptions, additional sensitivity analyses will be performed using transformations or alternate methods such as nonparametric or robust procedures.

### **9.5 Validation and Configuration Management**

Programs will be developed and maintained, and output will be verified according to processes described in procedures or technical manuals about the “Configuration Management of Statistical Analysis and Reporting Systems”, “Statistical Analysis and Reporting System Development and Validation”, and “Development of Statistical Analysis and Reporting Systems”.

Tables, figures and listings will be produced with validated standard macro programs where standard macros can produce the specified outputs.

The production environment consists of Amgen-supported versions of The SAS System running on the Sun Solaris operating system. Because it is common for multiple versions of SAS to be available during the study period, the SAS version used to produce analyses will be documented in the validation documentation and the clinical study report.

## **10. Statistical Methods of Analysis**

### **10.1 General Principles**

The analytical approach for this study will be to use inferential testing to evaluate the following:

- the effect of romosozumab treatment for 12 months followed by ALN treatment on fracture outcome as compared with ALN alone
- the effect of romosozumab treatment for 12 months on fracture outcomes as compared with ALN alone

All efficacy analyses will be performed by randomized treatment, regardless of actual treatment received.

At primary analysis, to maintain the overall significance level of 0.05, Hochberg's method will be used to evaluate the primary endpoints:

- Subject incidence of clinical fracture at primary analysis
- Subject incidence of new vertebral fracture through Month 24

If both the primary endpoints are significant at the 0.05 level (2-sided), each of the following secondary DXA BMD endpoints will be tested hierarchically at 0.05 (2-sided) according to the following sequence: percent change from baseline in BMD at lumbar spine at Month 24, percent change from baseline in BMD at total hip at Month 24, percent change from baseline in BMD at femoral neck at Month 24, percent change from baseline in BMD at lumbar spine at Month 12, percent change from baseline in BMD at total hip at Month 12, and percent change from baseline in BMD at femoral neck at Month 12.

If all preceding endpoints are significant, the nonvertebral fracture at the primary analysis will be evaluated based on a 1-sided test at the significance level determined by the alpha spending function specified in [Section 3.2.3](#). The adjusted 2-sided p-value will be provided to demonstrate the overall significance level of 0.05. All remaining secondary and exploratory efficacy endpoints will be explored at significance level of

0.05 (2-sided). If superiority of the nonvertebral fracture endpoint is achieved at the primary analysis and the study is stopped after the primary analysis has been performed, all data, including the additional safety and nonvertebral fracture data, collected after the primary analysis will be summarized descriptively. Study completion constitutes either completion of primary analysis if superiority is proven for nonvertebral fractures or until 440 subjects experience a nonvertebral fracture.

For analyses where the age stratification factor needs to be incorporated, the following general principles will be followed:

- For stratified analyses that are intended to evaluate the treatment effect, the analyses will be done using the randomized stratum, regardless of the subject's actual stratum. If the stratification error rate is  $> 5\%$ , a sensitivity analysis using the stratification factor of the actual value will be done for the primary efficacy endpoint.
- When the stratification factor is used as a covariate in the covariate analysis where the analysis interest is on the association between the covariate and the outcome, the stratification factor based on the actual value will be used.

Continuous parameters will be summarized using descriptive statistics, which include the mean, standard deviation, minimum, 25th percentile, median (50th percentile), 75th percentile, maximum, and number of non-missing observations (n). Nominal and ordinal categorical variables will be summarized using frequencies and percentages. Unless otherwise specified, the percentages will be based on the number of subjects in the specific analysis set for the endpoint. Time-to-event parameters will be summarized using the Kaplan-Meier event rates.

## **10.2 Subject Accountability**

The disposition of all randomized subjects will be tabulated by randomized treatment group. Subject enrollment and disposition for the number of subjects randomized, number of randomized subjects participating in the sub-study, successfully completing investigational product administration in the double-blind and overall study periods, and completing the study will be included. The disposition of subjects will also include the number of subjects who withdrew from the investigational product and their reasons for withdrawal for SC and oral investigation product. The disposition of the number of subjects who withdrew from study and their reasons for withdrawal will be provided.

### 10.3 Important Protocol Deviations

Important Protocol Deviations (IPDs) categories are defined by the study team before the first subject visit and updated during the IPD reviews throughout the study prior to database lock. These definitions of IPD categories, sub-category codes and descriptions will be used during the course of the study. The final IPD list is used to produce the Summary of IPDs table and the List of Subjects with IPDs. Important protocol violations including eligibility violations will be summarized and listed.

### 10.4 Demographic and Baseline Characteristics

The following demographic and baseline disease characteristics will be summarized by randomized treatment group based on all randomized subjects:

- Race
- Age (years)
- Age groups (<65, <75 and  $\geq 75$ )
- Years since menopause
- Body composition (height [cm], weight [kg], and BMI [kg/m^2])
- 10-year probability of major osteoporotic and hip fractures based on WHO risk factor criteria (FRAX) calculated with femoral neck BMD T-score
- 10-year probability of major osteoporotic and hip fractures based on WHO risk factor criteria (FRAX) calculated without femoral neck BMD T-score
- Fracture history including any fracture, osteoporotic fractures, vertebral fractures, nonvertebral fractures, major nonvertebral fracture, any historical fracture after age 55, and any historical fracture after age 45
- Presence or absence of severe vertebral fracture at baseline; based on most severe Genant semiquantitative grade at baseline on screening spinal radiograph)
- Number of prevalent vertebral fractures at baseline (0, 1, 2,  $\geq 3$ ; based on screening spinal radiograph)
- Most severe Genant semiquantitative grade at baseline (based on screening spinal radiograph)
- BMD T-score of lumbar spine, total hip, and femoral neck

- Selected laboratory analytes (calcium corrected by albumin, phosphorus, creatinine, estimated GFR, and estimated GFR level [ $< 15$ ,  $15$  to  $< 30$ ,  $30$  to  $< 60$ ,  $60$  to  $< 90$ , and  $\geq 90$  mL/min])
- Baseline serum 25 (OH) vitamin D level
- Prior use of any osteoporosis medication (yes, no)
  - Prior use of oral bisphosphonate (yes, no)
  - Prior use of intravenous bisphosphonate (yes, no)
  - Prior use of SERM (yes, no)
  - Prior use of PTH or PTH derivatives (yes, no)
  - Prior use of hormone replacement therapy (yes, no)
  - Prior use of calcitonin (yes, no)
  - Prior use of strontium (yes, no)
  - Prior use of fluoride (yes, no)
  - Prior use of calcitriol (yes, no)
  - Prior use of denosumab (yes, no)
- Baseline use of calcium and vitamin D (yes, no)
- Substance use during the past 5 years including tobacco use (never, former, and currently); alcoholic beverages (none,  $\leq 2$  per day,  $\geq 3$  per day);

#### 10.4.1 Vitamin D Loading Dose Administration

Subjects with a serum 25 (OH) vitamin D level  $\geq 20$  ng/mL and  $\leq 40$  ng/mL at screening were to receive an initial loading dose of 50,000 to 60,000 IU vitamin D after randomization. Receipt of this loading dose will be summarized by baseline vitamin D level ( $< 20$  ng/mL,  $\geq 20$  ng/mL and  $\leq 40$  ng/mL, and  $> 40$  ng/mL) and randomized treatment group. Baseline vitamin D level is based on the last screening level prior to randomization. The loading dose will be identified based on the concomitant medication eCRF as follows:

1. Select vitamin D medication records with start date within 1 week of Study Day 1
2. Derive dose per day and total dose as:
  - a. If dose  $\geq 50,000$  IU then dose per day and total dose are set to recorded dose

b. If dose < 50,000 IU then do the following to derive the total dose received:

i. If duration is missing or greater than 7 days, set duration to 7 days

ii. Dose per day and total dose are derived as follows based on recorded dose, frequency, and duration:

Frequency	Frequency code	Dose Per Day (DPD)	Total Dose
PER YEAR	PA	CMDOSE	CMDOSE
EVERY 2 MONTHS	Q2M	CMDOSE	CMDOSE
EVERY 2 WEEKS	Q2S	CMDOSE	CMDOSE
EVERY 3 MONTHS	Q3M	CMDOSE	CMDOSE
EVERY 3 WEEKS	Q3S	CMDOSE	CMDOSE
EVERY 4 WEEKS	Q4S	CMDOSE	CMDOSE
EVERY 6 MONTHS	Q6M	CMDOSE	CMDOSE
EVERY 6 WEEKS	Q6S	CMDOSE	CMDOSE
EVERY 8 MONTHS	Q8S	CMDOSE	CMDOSE
EVERY 8 WEEKS	Q8W	CMDOSE	CMDOSE
EVERY MONTH	QM	CMDOSE	CMDOSE
EVERY WEEK	QS	CMDOSE	CMDOSE
ONCE	ONCE	CMDOSE	CMDOSE
IMMEDIATELY	STAT	CMDOSE	CMDOSE
AT BEDTIME	HS	CMDOSE	DPD*duration
AS NEEDED	PRN	CMDOSE	DPD*duration
DAILY	QD	CMDOSE	DPD*duration
TWICE PER DAY	BID	CMDOSE * 2	DPD*duration
EVERY 12 HOURS	Q12H	CMDOSE * 2	DPD*duration
TWICE PER WEEK	BIS	CMDOSE * 2/7	DPD*duration
EVERY HOUR	QH	CMDOSE * 24	DPD*duration
EVERY 8 HOURS	Q8H	CMDOSE * 3	DPD*duration
3 TIMES PER DAY	TID	CMDOSE * 3	DPD*duration
THREE TIMES A WEEK	TIS	CMDOSE * 3/7	DPD*duration
EVERY 6 HOURS	Q6H	CMDOSE * 4	DPD*duration
4 TIMES PER DAY	QID	CMDOSE * 4	DPD*duration
4 TIMES PER WEEK	QIS	CMDOSE * 4/7	DPD*duration

Frequency	Frequency code	Dose Per Day (DPD)	Total Dose
EVERY 4 HOURS	Q4H	CMDOSE * 6	DPD*duration
EVERY OTHER DAY	QOD	CMDOSE / 2	DPD*duration
EVERY 3 DAYS	Q3D	CMDOSE / 3	DPD*duration
EVERY 4 DAYS	Q4D	CMDOSE / 4	DPD*duration

Page 2 of 2

3. Sum all total dose records for each subject to get total daily dose
4. Subjects with a total daily dose  $\geq 50,000$  IU will be considered as having received the loading dose of vitamin D

For subjects who enrolled in the sub-study, demographics, body composition, baseline BMD, and the following baseline laboratory data will also be summarized:

- Bone turnover markers (CTX, OC, BSAP, and P1NP)
- Selected laboratory analytes (calcium corrected by albumin, phosphorus, and iPTH)

## 10.5 Efficacy Analyses

The age stratification factor will be included in the statistical models when analyzing data from the entire study but will not be included in analyses of sub-study.

### 10.5.1 Descriptions of Standard Summaries and Statistical Models

#### 10.5.1.1 Standard Analyses for Binary Endpoints

All binary endpoints will be summarized using the number and percentage of subjects having the response of interest by treatment group. Unless otherwise specified, the percentages will be based on the number of subjects in the specific analysis set for the endpoint.

Treatment comparisons on binary endpoints will be done using a logistic regression model (Agresti, 1990) with treatment as the main effect (using control arm as the reference category) and age stratification, baseline total hip BMD T-score, and presence or absence of severe vertebral fracture at baseline as covariate to assess the significance of the treatment difference between treatment arm and control arm. The odds ratio and the corresponding 95% 2-sided confidence interval and p-values using a

score test will be provided. In the case that the logistic regression model does not converge due to sparse data or separation, a conditional logistic regression stratified by age strata, and baseline total hip BMD T-score and presence or absence of severe vertebral fracture at baseline will be used. This will also apply to other analyses using logistic regression in this analysis plan (SAS code in [Section 13.4.1](#))

In addition to the estimate of the odds ratio from the logistic regression model, point estimates of absolute risk reduction (difference in proportions, control – treatment) and risk ratio (ratio of proportions, treatment over control) as well as the corresponding 95% confidence intervals will also be calculated via the Mantel-Haenszel method ([Agresti and Hartzel, 2000](#)) adjusting for age strata, total hip BMD T-score ( $\leq -2.5$  and  $> -2.5$ ), and presence or absence of severe vertebral fracture at baseline (SAS code in [Section 13.4.1](#), [Section 13.4.2](#) and [Section 13.4.3](#)).

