## 7.9 Subgroup Analyses

The new vertebral fracture through Month 12 or Month 24, clinical fracture and nonvertebral fracture through Month 12 or at primary analysis, will be analyzed within each of the following subgroups:

- Age ( $< 75$  years,  $\geq 75$  years)
- Presence or absence of severe vertebral fracture at baseline (based on most severe Genant semiquantitative grade at baseline on screening spinal radiograph)
- Number of prevalent vertebral fractures at baseline (0-1, 2,  $\geq 3$ ; based on screening spinal radiograph)
- Race (White and non-White)
- Geographic region
  - Western Europe and New Zealand/Australia
  - Central and Eastern Europe and Middle East
  - Asia Pacific and South Africa
  - North America
  - Central/Latin America
- Central/Latin America and all regions excluding Central/Latin America
- Baseline lumbar spine BMD T-score ( $\leq -3$ ,  $> -3$  and  $\leq -2.5$ ,  $> -2.5$ )
- Baseline total hip or femoral neck BMD T-score  $\leq -3$  vs both total hip and femoral BMD T-score  $> -3$

- Baseline BMI (tertiles)
- FRAX score for major osteoporotic fracture (tertiles)
- History of nonvertebral fracture at age  $\geq 55$  years (yes, no)

The percent changes from baseline in lumbar spine BMD and total hip BMD at month 12 and month 24 will be analyzed by the following subgroups:

- Age ( $< 75$  years,  $\geq 75$  years)
- Geographic region
- Baseline lumbar spine BMD T-score ( $\leq -3$ ,  $> -3$  and  $\leq -2.5$ ,  $> -2.5$ ; for lumbar spine BMD analysis only)
- Baseline total hip BMD T-score ( $\leq -3$ ,  $> -3$  and  $\leq -2.5$ ,  $> -2.5$ ; for total hip BMD analysis only)

These subgroups, except for age strata, will be re-examined for appropriateness and may be re-categorized or omitted (due to small sample size, for example, if there are  $< 10\%$  of subjects within a subgroup) before unblinding. The analyses of these subgroups will be exploratory in nature.

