### 13.4 Code Fragments

CCI

CCI

CCI

CCI

CCI

CCI

CCI

CCI

CCI

CCI

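### The SAP's fallback for a non-converging logistic model gives no finite odds ratio when one arm has no events, and it does not say how the hip T-score is stratified

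*SAP*

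**What the plan says.** SAP 10.5.1.1 compares binary endpoints by logistic regression with treatment as main effect and "age stratification, baseline total hip BMD T-score, and presence or absence of severe vertebral fracture at baseline as covariate". No T-score categories are given there. The promised output is stated as "The odds ratio and the corresponding 95% 2-sided confidence interval and p-values using a" score test.

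The fallback has a stated trigger: "In the case that the logistic regression model does not converge due to sparse data or separation". The replacement is "a conditional logistic regression stratified by age strata, and baseline total hip BMD T-score and presence or absence of severe vertebral fracture at baseline". Again no T-score categories are given, and neither exact nor penalised inference is mentioned. The scope is wide: "This will also apply to other analyses using logistic regression in this analysis plan".

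The next paragraph of 10.5.1.1 adds a Mantel-Haenszel risk difference and risk ratio. For that analysis the total hip T-score is split into two categories, at or below -2.5 and above -2.5. The SAS code for this section is in SAP 13.4, which is redacted.

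**The concern.** There are two difficulties.

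**Treatment separation.** Separation is a named trigger. If it arises because one arm has no events, conditioning on strata removes the covariates but leaves the treatment coefficient, which is the parameter that diverges. The rule would then replace one model with no finite estimate by another.

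**T-score strata.** If the uncategorised T-score defines strata jointly with age group and severe fracture, many strata hold one or a few women. A stratum with only one arm, or with no event, contributes nothing to a conditional analysis. Precision would be lost in the sparse comparisons for which the fallback exists.

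At stake are the sparse secondary, exploratory and subgroup logistic analyses: new vertebral fracture by subgroup at Months 12 and 24, the treatment-by-subgroup interaction tests of SAP 10.5.2.4, and multiple new or worsening vertebral fracture. No confirmatory conclusion is at stake.

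**Working it through.** **Inputs from the documents (SAP 3.2.1 to 3.2.3).** 2,000 women per arm; new vertebral fracture on ALN 2.2% at one year and 4.4% at two; a 50% reduction, hence 1.1% and 2.2% on romosozumab/ALN; dropout 10% in year 1 and 8% in year 2, leaving 2,000 × 0.90 × 0.92 = 1,656 per arm.

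**Assumptions, not in the documents.** T-score mean -2.8 and SD 0.6 to 0.9; about half of the women aged 75 or over; about half with a severe fracture; T-score recorded to 0.1, 0.01 or 0.001.

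**1. The plan's own figure.** The documents give no figure for the fallback. The nearest is 95% power for new vertebral fracture after the Hochberg adjustment. With pooled rate 0.033, the null SE is √(2 × 0.033 × 0.967 / 2,000) = 0.00565 and the alternative SE is √((0.044 × 0.956 + 0.022 × 0.978) / 2,000) = 0.00564. At two-sided 0.025 (z = 2.241), power = Φ((0.022 − 2.241 × 0.00565) / 0.00564) = Φ(1.66) = 0.951. A Hochberg simulation gave 96.6% with 2,000 per arm and 94.9% with 1,800. The stated 95% is reproduced and is not in dispute.

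**2. Treatment separation.** In a stratum with a women on romosozumab, b on ALN and m events, of which x are on romosozumab, the conditional likelihood is

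L(β) = C(a,x) C(b,m−x) e^(βx) / Σ_k C(a,k) C(b,m−k) e^(βk).

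If x = 0 in every stratum, the numerator is constant and the denominator grows with β, so L keeps rising as β falls and has no maximum. If the T-score and severe fracture are instead kept as covariates within age strata, the same argument holds at any fixed value of their coefficients.

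Example: four strata of 50 per arm, 0 events against 6 (two strata with 2 events, two with 1).

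| β | 0 | −2 | −4 | −8 |
|---|---|---|---|---|
| log L | −4.18 | −0.77 | −0.11 | −0.002 |

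The score statistic is still finite. Expected events on romosozumab are 3, the variance is 2 × (2 × 0.25 × 98/99) + 2 × 0.25 = 1.490, and z = −3/√1.490 = −2.46. The exact one-sided p is (50 × 49 / (100 × 99))² × 0.5² = 0.0153. In simulation, every data set with an event-free arm (100%) also lacked a finite conditional estimate, whatever the T-score coding.

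**3. How often an arm has no events.** P(no romosozumab events) = (1 − rate)^n.

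| Women per arm | Month 12 (1.1%) | Month 24 (2.2%) |
|---|---|---|
| 2,000 | 2 × 10⁻¹⁰ | 5 × 10⁻²⁰ |
| 200 (a 10% subgroup) | 10.9% | 1.2% |

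**4. Information under literal T-score strata.** An event in a stratum of n women, with share p on romosozumab, contributes p(1−p). Under 1:1 allocation its expectation is 0.25(1 − 1/n), so a stratum of one keeps nothing and a stratum of two keeps half. If the number of other women in the stratum is Poisson with mean λ, the share kept is 1 − (1 − e^(−λ))/λ. With N women, precision d, T-score SD s and four age-by-severity cells, the average is λ = N d / (8 s √π). For N = 3,312, s = 0.7 and d = 0.01, λ = 3.34 and the share is about 71%. Simulation, which allows λ to vary across the T-score range, gives slightly less:

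| T-score coding | Full set, Month 24 | 10% subgroup, Month 24 | Subgroup data sets with no finite conditional estimate |
|---|---|---|---|
| −2.5 cut | 99.8% | 98% | 1% |
| 0.1 | 94–96% | 66–74% | 3% |
| 0.01 | 61–70% | 14–20% | 57% |
| 0.001 | 12–17% | about 2% | 99% |

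The last column (SD 0.7) counts all simulated data sets, not only those in which the main model would fail and the fallback would be used.

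**5. Covariate separation.** With no events in one level of severe fracture, a conditional model stratified on that factor gave a finite log odds ratio of −0.75 in the example. Here the fallback works.

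**The case against.** The strongest objection is that stratification on the raw T-score is only one reading. The comma after the age strata allows a model stratified by age that keeps the T-score and severe fracture as covariates. The stratified Cox model in SAP 10.5.1.3 has that form. On that reading step 4 falls away. The redacted code may also contain the -2.5 cut or an exact option, and redaction is not an omission. This stands, and it limits the T-score part to an ambiguity that needs settling. It does not rescue the rule under treatment separation, because step 2 holds on both readings. The age-only reading would also leave severe fracture as an estimated term, so separation on that factor would no longer be removed by conditioning.

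Second, the trigger is remote where it matters most, and the subgroup analyses are exploratory. SAP 7.9 adds that small subgroups "may be re-categorized or omitted (due to small sample size, for example". This also stands. But that wording permits removal without requiring it, and a subgroup just at the 10% example still meets an event-free romosozumab arm about one time in nine at Month 12.

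Third, the loss figures depend on T-score precision, SD and factor prevalence, none of which is given. At 0.1 precision the full-data loss is only 4% to 6%. For multiple vertebral fractures the documents state no expected rate, so how sparse that endpoint will be is unknown.

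A reader might infer that the fallback loses information or fails wherever it is needed. The documents do not support that. It can cure covariate separation, the score p-value survives treatment separation, and the Mantel-Haenszel risk difference is planned in any case.

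**Conclusion.** The point holds in a limited form and is minor. The SAP prescribes for separation a method that cannot return a finite odds ratio or a full 95% interval when one arm has no events. This follows from the form of the likelihood and needs no assumption beyond ordinary, non-exact conditional inference, which is all the visible text names.

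The T-score part is conditional. If the literal reading applies, about 4% of the information is lost in the full set at 0.1 precision and about 85% at 0.001, with larger losses in small subgroups. Both ends rest on the assumed SD, factor prevalences and precision.

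It would be wrong to infer that the new vertebral fracture result at Month 24 is at risk: the chance of no romosozumab events there is about 5 × 10⁻²⁰ at the planned rates. The effect is confined to sparse secondary, subgroup and exploratory logistic analyses.

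**What to change.** Replace the fallback sentence in SAP 10.5.1.1 with one of these:

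- **Firth penalised-likelihood logistic regression** with the same covariates as the main model, reporting a profile-likelihood interval and p-value. The cost is slight shrinkage of the odds ratio and a p-value that is no longer the score test named for the main model.
- **Conditional logistic regression** stratified by age group, severe fracture and total hip T-score at the -2.5 cut already used for Mantel-Haenszel, with exact conditional inference (median-unbiased estimate and exact interval) named for treatment separation. The cost is a conservative interval.

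Either is one sentence and a standard software option, and neither changes the primary analysis. If the code in SAP 13.4 already uses a T-score cut or exact inference, bring the sentence into line with it. For logistic models whose covariates differ from the standard set, the same sentence should say which covariates or strata the fallback uses.
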